8.1.3. Risks associated with study procedures

Study procedures may impose additional risks to study participants. In case of the SAFE Trial this theoretically could concern an increased risk for HSV infection of

- housemates, or
- other places than the extra-genital region

due to the frequent sampling and/ or touching of the extra-genital area.

HSV is transmitted via direct contact with infected secretions, such as during sexual intercourse. Casual contact, sharing of bathroom, toilet seats, etc. have not been implicated in HSV transmission. Furthermore, sampling and cream application is only done when participants are asymptomatic, which in principle is not different from normal hygienic or sexual behavior. Therefore, swabbing of the genital area by a study participant does not pose a risk to housemates.

The likelihood of spreading the virus to another part of the body is nil, since autoinoculation does not occur in persons who are infected outside of the primary episode as then immunity has been established. Of note, in that respect is that the University of Washington HSV research group has been using self-collected swabs for study of HSV for >25 years, and neither autoinoculation, nor exposure of housemates has ever been suspected as a result of these procedures.

In summary, the likelihood for imposing additional risks to study participants and their housemates due study procedures is considered negligible.

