8.2. Methods to Minimize Risk

Product handling and procedure guidance are provided in the Training Materials, and will be used for device training to minimize risks associated with device use.

Additionally, efforts will be made to minimize and/ or early capture of these possible risks through site/investigator selection and management. Site and investigator selection criteria are established to ensure that the study personnel and their institutions are qualified to screen, perform and manage the study procedures as well as support the associated requirements for research. Also trial management structure is designed to provide disciplined oversight of the trial activities including monitoring of site and personnel performance.

Site and investigator criteria include the following:

- Investigational site personnel must be experienced and skilled in treating participants with viral STI's.
- Good collaboration with general practitioners to ensure proper participant follow-up.
- The study site must have an adequately staffed research department with a minimum of one dedicated study coordinator.
- Able to enroll a minimum of 5 participants

Although the risk associated with the study procedures is considered negligible as compared to normal practice, the study participants will be instructed to wash their hands thoroughly after their (daily) sampling.

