Appendix 1: English master Informed Consent

Appendix 2: Daily Home PCR Instructions for Women

Thank you for volunteering for this study. Please read this sheet over carefully to understand how the study is being done.

Study Supplies

You will receive the following supplies:

- Dacron-tipped swabs (similar to Q-Tips®)
- Small plastic vials (with green, yellow, and red labels)
- Color coded labels
- A storage box
- VIBLOK cream
- Mirror
- A bag for transport
- A swab collection log
- A study diary

Sample Labels

The labels are preprinted with your study, clinic, and participant number. For each sample you collect, please fill in the date and time you collected the sample.

Study Diary

It is important that you bring your study diary to **each** clinic visit. Fill out the diary immediately before you obtain your swab samples. Please record this information as accurately as possible.

Storage of Samples

Vials with and without swabs can be stored at room temperature. When you return to the clinic for your next appointment, please bring the storage box with all the swab samples and your diary.

Communicating with the Clinic

If you develop symptoms of a recurrence or have any questions, please contact the **<specify the department>**. If you have ANY unusual urinary, genital, or rectal symptoms, such as a urinary tract infection, rash, or bleeding, call the clinic as soon as possible for an appointment. Every effort will be made to accommodate your schedule for clinic visits. Please call in at the earliest sign of symptoms so that a visit can be scheduled as soon as possible.

Weekdays: <specify contact information>

After Hours: <specify contact information>

Collecting Daily Swab Samples

Please read the following instructions carefully, it is very important that you collect samples in the same order as given in the instructions.

Please collect two extra-genital swabs per day: one **before** and one 5-60 minutes **after** VIBLOK application.

Please also collect a swab from a herpes **lesion** during an outbreak: do not apply VIBLOK when you develop a lesion and contact the clinic when you first notice symptoms.

Collect samples **once a day** before bathing or showering, or at least one hour after bathing or showering. Thoroughly wash and dry your hands before beginning.

[figure not shown]

Figure 2.1. Female genitals with VIBLOK application and swabbing area.

1/ To collect the **EXTRA GENITAL swab in the **green-labeled vial** **before** VIBLOK:**

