1. Unwrap 1 sterile swab and hold it by the plastic shaft. Try not to touch the Dacron tip with your hands.

2. Gently put the swab on your labia.
3. Rotate the swab in a full circle. Gently remove the swab from your labia.
4. Rub the same swab from the outer (hairy) edges of your labia to the smooth skin below the vaginal opening, covering the entire area.
5. Rub the swab over the skin between your vagina and anal opening (anus).
6. Rub the swab in a circular motion over your rectal area, covering a radius of about 1.0 cm around the anus.

2/ Closing the vials and labeling:

1. Place the collected swab into the vial with the **green color coded** label.

2. Pull the swab out of the vial 0.5 cm, break (or cut) off the end of the plastic shaft, and discard it in the trash.
3. Securely replace the screw top of the vial.
4. Complete the swab collection log, with the full date (for example: 17-AUG-2015) and time of collection.
5. Place the labeled vial inside the grid box.

3/ Apply VIBLOK

1. Apply one packet of VIBLOK™ evenly and thoroughly to all external genital (including labia and clitoris), pubic, and perianal areas with or without hair.
2. Ensure application from minimally 2 cm outside of the outer (hairy) edges of your labia to the smooth skin below the vaginal opening, covering the entire area, the skin between your vagina and anal opening (anus), and your rectal area, covering a radius of about 2.5 cm around the anus. Apply more than one packet if needed.
3. Wait 5 to 60 minutes.

4/ To collect the **EXTRA GENITAL** swab in the **yellow-labeled** vial after VIBLOK:

1. Repeat the procedure as described under 1/ and 2/ using the vial with the **yellow color coded label**
2. Make sure to rub the swap only in the area where you applied VIBLOK: Keep a distance of at least 1 cm to the outer edges.
3. Use the mirror from your sampling kit if needed.

5/ To collect a **LESION** swab in the **red-labeled** vial:

If you develop a herpes lesion, please rub a separate swab over this area and place the swab in one of the **red-labeled** vials. Do **not** apply VIBLOK when you develop a herpes lesion and call the clinic when you first notice symptoms.

Repeat the procedure as described under 2/.

6/ After collection of the swabs

After you have collected the daily swabs, ensure to

1. thoroughly wash and dry your hands
2. have completed the participant diary

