1. Unwrap 1 sterile swab and hold it by the plastic shaft. Try not to touch the Dacron tip with your hands.

2. Rub the swab, starting at the tip of the penis, over the whole length of the penis to the base, covering the entire area.
3. Rub the swab over the skin between your penis and anal opening (anus).
4. Rub the swab in a circular motion over your rectal area, covering a radius of about 1 cm around the anus.

2/ Closing the vials and labeling:

1. Place the collected swab into the vial with the **green color coded** label.

2. Pull the swab out of the vial 0.5 cm, break (or cut) off the end of the plastic shaft, and discard it in the trash.
3. Securely replace the screw top of the vial.
4. Complete the swab collection log, with the full date (for example: 17-AUG-2015) and time of collection.
5. Place the labeled vial inside the grid box.

3/ Apply VIBLOK

1. Apply one packet of VIBLOK™ evenly and thoroughly to all external genital, penile shaft, pubic and perianal areas – with or without hair, minimally 2 cm outside of the swabbing area.
2. Ensure application starting at the tip of the penis, over the whole length of the penis to the base, covering the entire area, the skin between your penis and anal opening (anus), and your rectal area, covering a radius of minimally 2,5 cm around the anus. Apply more than one packet if needed.
3. Wait 5 to 60 minutes.

4/ To collect the **EXTRA GENITAL** swab in the **yellow-labeled** vial after VIBLOK:

1. Repeat the procedure as described under 1/ and 2/ using the vial with the **yellow color coded** label
2. Make sure to rub the swap only in the area where you applied VIBLOK: Keep a distance of at least 1 cm to the outer edges.
3. Use the mirror from your sampling kit if needed.

5/ To collect a **LESION** swab in the **red-labeled** vial:

If you develop a herpes lesion, please rub a separate swab over this area and place the swab in one of the **red-labeled** vials. Do **not** apply VIBLOK when you develop a herpes lesion and call the clinic when you first notice symptoms.

6/ After collection of the swabs

After you have collected the daily swabs, ensure to

1. thoroughly wash and dry your hands
2. have completed the participant diary

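### The home swab sheets ask for no hand wash between applying VIBLOK and taking the after swab, so the two swabs of each pair are not handled alike

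*Protocol*

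**What the plan says.** Appendices 2 and 3 set out the daily sequence, with the same structure for women and men.

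- Before step 1: "Thoroughly wash and dry your hands before beginning".
- Step 1, before swab: "Unwrap 1 sterile swab and hold it by the plastic shaft. Try not to touch the Dacron tip with your hands".
- Step 2: put the swab in the vial, draw it out slightly, break or cut off and discard the end of the shaft, close the vial, complete the log.
- Step 3, cream. The women's sheet reads: "Apply one packet of VIBLOK™ evenly and thoroughly to all external genital (including labia and clitoris), pubic, and perianal areas with or without hair". The men's sheet covers the corresponding areas. The step ends, in both, with "Wait 5 to 60 minutes".
- Step 4, after swab: "Repeat the procedure as described under 1/ and 2/ using the vial with the" yellow label.
- Step 6: "After you have collected the daily swabs, ensure to", followed by washing and drying the hands and completing the diary.

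In the protocol body, section 8.2 says that "the study participants will be instructed to wash their hands thoroughly after their (daily) sampling".

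The performance endpoint is a within-person contrast. Protocol 9.1 and SAP 4.2.1 count the swabs positive only before the cream, subtract those positive only after it, and compare the result with zero by a Wilcoxon signed-rank test.

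**The concern.** A paired comparison is clean when the two measurements differ only in the intervention. Here they also differ in the state of the hands. The before swab comes straight after a wash. The after swab comes after the participant has worked cream over the skin that may be shedding, and the sheet asks for no wash in between. Application by hand is implied rather than stated.

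If virus reaches the second swab from the fingers, a day on which the cream worked is recorded as a day on which it did not. The analysis cannot separate the two: a both-positive pair caused by carry-over looks the same as one caused by failure of the barrier. The rules for implausible swab data in SAP 2.3 would not detect it. What is at stake is the secondary performance result.

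**Working it through.** **1. Where washing is asked for**

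| Point in the sequence | Action | Wash requested |
|---|---|---|
| Opening text | Prepare | Yes |
| Step 1 | Take before swab | No (follows the wash) |
| Step 2 | Close and label vial | No |
| Step 3 | Apply cream, wait | No |
| Step 4 | Repeat steps 1 and 2 for after swab | No |
| Step 6 | After all swabs | Yes |

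The opening wash stands ahead of step 1, so repeating steps 1 and 2 does not bring it back. What is repeated is the instruction to hold the shaft and try to avoid the tip.

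**2. Direction of any effect on detection**

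Score each day +1 if only the before swab is positive, −1 if only the after swab is positive, and 0 otherwise. Suppose virus transfer turns a negative after swab positive:

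- before positive, after negative: +1 becomes 0;
- before negative, after negative: 0 becomes −1;
- after swab already positive: no change.

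Every possible change lowers the person's score, so viral carry-over can only make the cream look less effective. For copy number, added virus on after samples narrows the difference if all positive samples count (Protocol 9.5.2). SAP 4.2.1 uses only days positive on one side, and there the direction is less certain.

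**3. Illustrative size**

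The plan states no figure for carry-over, so there is none to reproduce. Inputs from Protocol 9.1 and SAP 1.4 are 8% of days shedding, a 50% reduction (so 4% after), 40 participants and 28 days. That gives 40 × 28 = 1,120 pairs, with 89.6 before positives and 44.8 of them cleared. Let c be the share of cleared after swabs made positive again. The value of c is assumed.

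*After positives only on before-positive days:* after rate = 4% + c × 4%; apparent reduction = 1 − after rate / 8%.

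| c | Pairs changed (44.8 × c) | After rate | Apparent reduction |
|---|---|---|---|
| 5% | 2.24 | 4.2% | 47.5% |
| 10% | 4.48 | 4.4% | 45% |
| 25% | 11.2 | 5.0% | 37.5% |

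*Before and after swabs independent within a person (an extreme case):* 96% of before-positive days have a negative after swab, so after rate = 4% + c × 8% × 96% = 4% + 7.68% × c. At c = 10% this is 4.768%, an apparent reduction of 40.4%. At c = 25% it is 5.92%, or 26.0%.

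*Power.* The two-sided signed-rank test was simulated with 40 participants and 28 days, 1,500 trials per setting. Shedding rates were either the same for everyone or beta-distributed with mean 8% and precision 5, 1 or 0.5. The spread is also an assumption. Ranges are across these settings.

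| Model | Power at c = 0 | Power at c = 25% |
|---|---|---|
| After positives only on before-positive days | 83% to 100% | 78% to 100% |
| Independent swabs | 73% to 97% | 54% to 61% |

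**The case against.** The strongest reply is that contamination needs a handling slip. The second swab is sterile, is held by its shaft with the tip kept clear of the fingers, and has the end of its shaft discarded. It is then rubbed over the same skin the hands touched, so only the extra transfer from hand to tip matters. This stands as a reason to expect a small effect. It does not remove the difference in handling: the participant is told only to try to avoid the tip, and step 2 has the fingers working close to the vial mouth.

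The sheets are also silent rather than prohibitive. A reader might infer that participants must go from cream to swab unwashed, because the sheets stress order. That stress concerns the order in which samples are collected. It does not stop anyone washing during the wait, and some probably will. The Instructions for Use (Protocol 2.1), the instruction video and the observed first session (Protocol 5.2.3) may include a wash. They are not among the documents, so the finding is about the text of the two appendices.

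A reader might also see a failed hygiene control, since section 8.1.3 raises a theoretical infection risk "due to the frequent sampling and/ or touching of the extra-genital area" and section 8.2 answers with washing only after sampling. The documents do not support this. Both sections rate the added risk as negligible, 8.1.3 gives reasons, and 8.2 offers the wash as an extra precaution. Section 8.2 needs no change on this account.

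Finally, no carry-over share has any basis in the documents. That is correct, and the figures above show sensitivity only.

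**Conclusion.** The omission is real and identical in both appendices. It leaves an avoidable difference in handling between the two swabs of each pair. Transfer by hand is possible, not shown, and its size is unknown. For detection, any transferred virus would understate the cream's performance and could not create a false benefit. Cream residue on the hands could also reach the swab, with an effect the documents do not let us judge.

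It would go too far to conclude that the performance result is materially biased or the test underpowered. When after positives occur only on before-positive days, even an assumed 25% carry-over costs little power. The large losses need the independence model as well. The primary endpoint, SADE incidence, is untouched. This is a minor point, worth acting on because prevention is simple and carry-over cannot be corrected at analysis.

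**What to change.** In step 4 of Appendices 2 and 3, before the second swab is unwrapped, add the wash-and-dry instruction that already opens the daily procedure. Placing it there, rather than at the end of step 3, also covers anything touched during the wait. Check the Instructions for Use and the training video, and align them if they differ.

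The cost is one extra hand wash a day for each participant and one added line per sheet, handled as a minor document revision under Protocol 11.6, with ethics committee approval where required. No extra visits, participants or changes to the analysis are needed.

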Appendix 3: Daily Home PCR Instructions for Men

Thank you for volunteering for this study. Please read this sheet over carefully to understand how the study is being done.

Study Supplies

You will receive the following supplies:

- Dacron-tipped swabs (similar to Q-Tips®)
- Small plastic vials (with green, yellow, and red labels)
- Color coded labels
- A storage box
- VIBLOK cream
- Mirror
- An bag for transport
- A swab collection log
- A study diary

Sample Labels

The labels are preprinted with your study, clinic, and participant number. For each sample you collect, please fill in the date and time you collected the sample.

Study Diary

It is important that you bring your study diary to **each** clinic visit. Fill out the diary immediately before you obtain your swab samples. Please record this information as accurately as possible.

Storage of Samples

Vials with and without swabs can be stored at room temperature. When you return to the clinic for your next appointment, please bring the storage box with all the swab samples and your diary.

Communicating with the Clinic

If you develop symptoms of a recurrence or have any questions, please contact the **<specify the department>**. If you have ANY unusual urinary, genital, or rectal symptoms, such as a urinary tract infection, rash, or bleeding, call the clinic as soon as possible for an appointment. Every effort will be made to accommodate your schedule for clinic visits. Please call in at the earliest sign of symptoms so that a visit can be scheduled as soon as possible.

Weekdays: <specify contact information>

After Hours: <specify contact information>

Collecting Daily Swab Samples

Please read the following instructions carefully, it is very important that you collect samples in the same order as given in the instructions.

Please collect two extra-genital swabs per day: one **before** and one 5-60 minutes **after** VIBLOK application.

Please also collect a swab from a herpes **lesion** during an outbreak: do not apply VIBLOK when you develop a lesion and contact the clinic when you first notice symptoms.

Collect samples **once a day** before bathing or showering, or at least one hour after bathing or showering. Thoroughly wash and dry your hands before beginning.

VIBLOK application area (grey area)

[figure not shown]

Figure 3.1. Male genitals with VIBLOK application and swabbing area.

1/ To collect the **EXTRA GENITAL swab in the **green-labeled vial before VIBLOK:****

1. Unwrap 1 sterile swab and hold it by the plastic shaft. Try not to touch the Dacron tip with your hands.

2. Rub the swab, starting at the tip of the penis, over the whole length of the penis to the base, covering the entire area.
3. Rub the swab over the skin between your penis and anal opening (anus).
4. Rub the swab in a circular motion over your rectal area, covering a radius of about 1 cm around the anus.

2/ Closing the vials and labeling:

1. Place the collected swab into the vial with the **green color coded** label.

2. Pull the swab out of the vial 0.5 cm, break (or cut) off the end of the plastic shaft, and discard it in the trash.
3. Securely replace the screw top of the vial.
4. Complete the swab collection log, with the full date (for example: 17-AUG-2015) and time of collection.
5. Place the labeled vial inside the grid box.

3/ Apply VIBLOK

1. Apply one packet of VIBLOK™ evenly and thoroughly to all external genital, penile shaft, pubic and perianal areas – with or without hair, minimally 2 cm outside of the swabbing area.
2. Ensure application starting at the tip of the penis, over the whole length of the penis to the base, covering the entire area, the skin between your penis and anal opening (anus), and your rectal area, covering a radius of minimally 2,5 cm around the anus. Apply more than one packet if needed.
3. Wait 5 to 60 minutes.

4/ To collect the **EXTRA GENITAL** swab in the **yellow-labeled** vial after VIBLOK:

1. Repeat the procedure as described under 1/ and 2/ using the vial with the **yellow color coded** label
2. Make sure to rub the swap only in the area where you applied VIBLOK: Keep a distance of at least 1 cm to the outer edges.
3. Use the mirror from your sampling kit if needed.

5/ To collect a **LESION** swab in the **red-labeled** vial:

If you develop a herpes lesion, please rub a separate swab over this area and place the swab in one of the **red-labeled** vials. Do **not** apply VIBLOK when you develop a herpes lesion and call the clinic when you first notice symptoms.

6/ After collection of the swabs

After you have collected the daily swabs, ensure to

1. thoroughly wash and dry your hands
2. have completed the participant diary

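### At the tip of the penis, and wherever home application is incomplete, the limits placed only on the 'after' swab can make it sample less skin than the 'before' swab, always in favour of the cream

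*Protocol*

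**What the plan says.** Protocol Appendices 2 (women) and 3 (men) set out a daily sequence of 'before' swab, cream, a wait of 5 to 60 minutes, and 'after' swab. The quotes below are from Appendix 3.

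- **Step 1, 'before' swab (men):** "Rub the swab, starting at the tip of the penis, over the whole length of the penis to the base", then the skin back to the anus, and around it "covering a radius of about 1 cm around the anus". No margin or limit is attached.
- **Step 3, cream (men):** "minimally 2 cm outside of the swabbing area", and around the anus "covering a radius of minimally 2,5 cm around the anus". On the penis: "Ensure application starting at the tip of the penis, over the whole length of the penis to the base". A second packet is allowed if needed.
- **Step 4, 'after' swab:** first "Repeat the procedure as described under 1/ and 2/ using the vial with the" yellow label; then "Make sure to rub the swap only in the area where you applied VIBLOK" and "Keep a distance of at least 1 cm to the outer edges".

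Appendix 2 has the same step 4. For women the cream goes at least 2 cm beyond the outer labial edge and to a radius of about 2.5 cm around the anus. The swab goes to the labial edge and to about 1.0 cm around the anus.

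SAP sections 1.3, 4.2.1 and 4.2.2 count, for each person, the swabs positive only before the cream minus those positive only after. They test this difference against zero with the Wilcoxon signed-rank test and read an average above zero as a protective effect. SAP section 1.5 describes the study as single-arm and open-label.

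**The concern.** The detection endpoint is a within-day comparison of two swabs. It measures the cream only if both swabs sample the same skin. Two limits apply to the second swab alone, and each can only take skin away from it. Virus lying solely on skin that the first swab touches and the second skips gives a day positive only before the cream, even if the cream does nothing. A real effect would be overstated in the same way.

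The data could not show this afterwards. There is no control arm or sham application. The diary (Appendix 4) records swab times but not coverage, and SAP section 3.5 measures compliance by returned packages. Because one of the two routes affects men only, the comparison between men and women in SAP section 4.3.2 could also be tilted.

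**Working it through.** **1. Does the 1 cm rule cut into the 'before' path when the instructions are followed?**

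Inputs are the distances in steps 1, 3 and 4. Slack = (cream extent - 1 cm) - swab extent. Zero or more means no skin is lost.

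| Boundary | Cream extent | Less 1 cm | Swab extent | Slack |
|---|---|---|---|---|
| Around the anus, both sexes | 2.5 cm | 1.5 cm | about 1.0 cm | +0.5 cm |
| Outer labial edge (women) or edge of swab area (men), measured beyond that edge | 2.0 cm | 1.0 cm | 0 cm | +1.0 cm |
| Tip of the penis, measured beyond the tip | 0 cm | -1.0 cm | 0 cm | -1.0 cm |

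At every boundary with a stated margin the slack is positive, so the limits remove nothing. The tip is the exception: cream and swab both begin there and no margin beyond it is possible. The first sentence of step 4 sends the man back to the tip. The edge rule, if he counts the tip as an edge of the creamed area, starts him 1 cm short.

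**2. What if application is incomplete?**

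If the cream extends m cm beyond the swab area, the slack there is m - 1, which is negative once m is below 1 cm. An uncreamed gap inside the path is excluded outright by the creamed-skin rule. Neither limit applies to the 'before' swab, so the loss has one direction.

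**3. What could it do to the detection endpoint?**

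From the documents: 40 participants, 28 days, 8% positivity, two-sided 5% test (2.5% in the protective direction).

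Assumed, because the documents give no values:
- an inert cream;
- single-swab sensitivity s = 80%;
- 20 of the 40 are men and all 20 are affected;
- f, the share of an affected man's shedding days on which virus lies only on the skipped skin, is 5%, 10% or 20%.

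Per true shedding day:
- P(positive before only) = s × [1 - s(1 - f)]
- P(positive after only) = (1 - s) × s(1 - f)
- Difference = s × f

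True shedding is 0.08 / 0.80 = 10% of days. The expected net pre-only count per affected man is therefore 28 × 0.10 × 0.80 × f = 2.24f.

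| f | Net per affected man | Net over 20 men | Apparent reduction, all 40 (f × 20/40) | False 'protective' result (simulated) |
|---|---|---|---|---|
| 5% | 0.112 | 2.24 | 2.5% | about 5% |
| 10% | 0.224 | 4.48 | 5% | 10-12% |
| 20% | 0.448 | 8.96 | 10% | about 24% |

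The last column is a simulation of the planned signed-rank test. Separate runs of the half-affected setting gave 5-6%, 8-12% and 23-25%. With 16 men, the minimum for the less represented sex in Protocol section 4, the figures are about 5%, 6-7% and 18-20%.

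For scale, the planned 50% reduction corresponds to 40 × 28 × 0.08 × 0.5 = 44.8 net swabs. The artefact is small against that target. It matters more for whether the test rejects than for the size of a large effect.

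**The case against.** The strongest reply is that step 3 already supplies the margin. Cream is spread past the swab path so that the second swab can cover the same path and still stay off the uncreamed border. This is correct at every boundary with a stated distance. A reader might infer from step 4 alone that the 'after' swab always samples less skin. The documents do not support that: a participant who follows them loses nothing except, on a literal reading, at the tip.

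Other replies have partial force:

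- **The tip is only a reading ambiguity.** The edge rule is naturally read as keeping off neighbouring uncreamed skin. Figure 3.1, captioned as showing the application and swabbing area, is not available in the text reviewed and may settle it. How many men would start short is unknown. The written conflict remains.
- **Gaps are an adherence matter.** Protocol sections 5.2.3 and 5.2.4 provide an instruction video, a supervised first sequence and a call after 2-5 days; the kit includes a mirror. These reduce the problem. They do not change its direction, and nothing indicates how well participants can see gaps and steer round them.
- **The limits serve a purpose.** They keep the second swab on covered skin, so that the barrier is measured rather than application coverage. This is a fair reason to keep a margin, but not to apply it to one swab only.
- **Large error rates are not established.** With every participant affected, f of 10% or 20% gives about 27% and 71-74% at 80% sensitivity, and 75% or more if the swabs otherwise agree perfectly. Those figures need an unsourced f in both sexes, whereas the only route that survives correct application affects men. Also, f requires virus on the skipped skin and nowhere else on the path, which is stricter than skipping some skin.

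**Conclusion.** The point holds in a limited form. The instructions for the two swabs are not identical. The difference has no effect where the cream reaches its stated margins. It can take skin from the 'after' swab at the tip of the penis, where two sentences of step 4 conflict if read literally, and in either sex where home application is incomplete. Any loss favours the cream and cannot be detected in this design.

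The size is unknown because the documents give no basis for f. Under the stated assumptions (inert cream, 80% sensitivity, 20 of 40 affected), the chance of a false protective finding rises from a nominal 2.5% to about 5%, 10-12% and 24% for f of 5%, 10% and 20%. These figures are illustrations, not estimates. If few men read the edge rule literally, the effect is close to nil.

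Severity is minor to moderate. Detection is a secondary endpoint, and the primary safety endpoint and the study's success rule are untouched.

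**What to change.** In Appendices 2 and 3, state that the 'before' and 'after' swabs follow one identical path with identical limits and, for men, that both start at the same point at the tip. If a margin is kept, define it on the anatomy rather than on the edge of the cream, and write it into step 1 as well as step 4. Teach the common path in the supervised Visit 1 session and the instruction video, and check that Figure 3.1 agrees.

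The cost is a few sentences in two appendices and in the training material. No change to the sample size or the planned test is needed. There is a small downside: the 'after' swab may touch thinly creamed skin, or both swabs may cover slightly less skin if a common margin is used, so the performance figure may look slightly less favourable. The change has to be in place before swabs are collected, because coverage is not recorded and comparability cannot be restored afterwards.
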